12.4 Records and Reports

12.4.1 Responsibilities of the Sponsor

The Sponsor and CRO are responsible for maintaining study records and reports per applicable ICH GCP, federal regulations, ISO 14155, and applicable standard operating procedures (SOPs), and study-specific plans (e.g., Monitoring Plan, Data Management Plan, Training Plan, and Statistical Analysis Plan).

12.4.2 Responsibilities of the Investigator

The investigator will maintain the following accurate, complete, and current records relating to their participation in the study:

- All correspondence which pertains to the investigation

- Records of each subject's case history and exposure to the device. Case histories include the case report forms and supporting data including, for example, signed and dated ICFs and medical records including, for example, progress notes of the physician, the individual's hospital chart(s), and the nurses' notes. Such records will include:
 - Documents evidencing the informed consent process. The case history for each individual will document that informed consent was obtained prior to participation in the study.
 - All relevant observations, including records concerning adverse device effects (whether anticipated or unanticipated), information and data on the condition of each subject upon entering, and during the course of, the investigation, including information about relevant previous medical history and the results of all diagnostic tests
 - A record of the exposure of each subject to the investigational device, including the date and time of each use, and any other therapy
- The protocol, with documents showing the dates of and reasons for each deviation from the protocol
- Signed Investigator Agreements, financial disclosure agreements, PI protocol signature pages, and curriculum vitae
- IRB approval documents, including approval of protocol, protocol amendments and ICFs

The investigator is responsible for the preparation, review, signature, and submission of the reports listed below in Table 3.

The remainder of this page is internationally left blank.

Table 3: Investigator Reporting Responsibilities

Report	Submitted to	Description
Unanticipated Serious Adverse Device Effects (USADE)	Sponsor/CRO & IRB	Notification within 10 working days after the investigator first learns of the effect.
Serious Adverse Events	IRB	Per IRB reporting requirements
Withdrawal of IRB approval	Sponsor/CRO	Notification within 5 working days of withdrawal.
Progress Report	Sponsor/CRO & IRB	Periodic report detailing the progress of the study, occurring at least annually.
Deviations from protocol (CFR 812.150)		
Emergency Use	Sponsor/CRO & IRB	Notification must be made within 5 working days of the occurrence of an emergency deviation (made to protect the life or physical well-being of a subject).
Other	Sponsor/CRO & IRB	If the deviation affects scientific soundness of the study or the rights, safety, or welfare of the subject (and is not an emergency), prior approval must be obtained from Monteris, the reviewing IRB, and FDA when required.
Failure to obtain informed consent	Sponsor/CRO & IRB	Notification within 5 working days
Final Report	Sponsor/CRO & IRB	Submitted within 3 months after termination or completion of the investigation.

12.5 Study Documentation

12.5.1 Case Report Forms

Study data will be collected using CRFs in an electronic data capture system. Further information regarding CRFs is found in the study-specific CRF Completion Guidelines.

12.5.2 Record Storage and Retention

The investigator will maintain all study documentation as outlined in the Clinical Trial Agreement.

12.5.3 Data Management

Study data will be managed as outlined in the study-specific Data Management Plan.

12.6 Study Monitoring

Each Site will be monitored by the Sponsor and/or CRO to ensure that the study is conducted in compliance with the protocol, and in accordance with good clinical practices, CRO SOPs and the study-specific Monitoring Plan.

12.7 Ethical Conduct of the Study

This study is to be conducted in accordance with US and international standards for good clinical practice, as described in the following documents:

- International Conference on Harmonisation Guidelines for Good Clinical Practice (1996)
- US Code of Federal Regulations (CFR) regarding clinical studies (21 CFR including parts 50, 54 and 56 and 812)
- ISO 14155: 2011

12.8 Institutional Review Board

The Site must submit the protocol and ICF to the IRB and will forward a copy of the written approval to the CRO. The study (study number, protocol title, and version), documents approved (e.g., protocol, ICF) and the date of the review should be clearly stated on the IRB approval documentation, and the approval must be signed by the IRB Chair. The Site will not be activated to enroll subjects until a copy of written and dated approval has been received by the CRO and other applicable study activation requirements (as outlined in the Monitoring Plan) are complete.

The Site must submit any protocol or ICF amendments to the IRB and is required to forward a copy of the written approval to the CRO. The IRB should also be informed of any event likely to affect the safety of subjects or the conduct of the study.

The ICF must be reviewed by the CRO prior to submission to the IRB for approval.

12.9 Protocol Deviations

A protocol deviation is defined as a circumstance in which the investigator or other Site personnel did not conduct the trial according to the protocol, applicable laws/regulations, or any study agreements (e.g., Clinical Trial Agreement or Investigator Agreement).

Every attempt will be made to adhere to the protocol. However, should an investigator be required to deviate from the protocol to protect the life or physical well-being of a study subject in an emergent circumstance, such notice will be given to the Sponsor or CRO as soon as possible, but no more than 5 working days from the date the emergency occurred. With the exception of an emergent circumstance, prior approval from the Sponsor and the IRB is required for any change in, or deviation from, the protocol as such changes may affect the scientific soundness of the protocol or the rights, safety, and welfare of study subjects.

Protocol deviations will be documented on the *Protocol Deviation* CRF. Deviations are reportable to the Institution's governing IRB during the annual reporting process, unless otherwise directed by the governing IRB requirements.

12.10 Study Discontinuation

The Sponsor reserves the right to terminate or suspend the study for valid scientific reasons or reasons related to the protection of subjects (e.g., the discovery of an unexpected, significant, or unacceptable

risk to subjects). The Sponsor may also terminate or suspend the study if the stopping rules (as defined in the DSMB charter) have been met.

If the study is terminated prematurely or suspended, the Sponsor will promptly inform all investigators of the termination or suspension and the reason(s). The IRB will also be informed, either by the Sponsor or investigator, and provided with the reason(s) for the termination or suspension. If applicable, regulatory authorities will be informed.

The IRB may choose to discontinue the study at any Site for which they granted approval if the research study is not conducted in accordance with the IRB's requirements or the research study indicates unexpected serious harm to subjects.

The remainder of this page is internationally left blank.

APPENDIX A MEDICATIONS

All prescription medications (epilepsy and non-epilepsy) that the subject is taking during the course of the trial will be recorded on a CRF. Epilepsy medications will be recorded on the *Epilepsy Medication Log* CRF. Non-epilepsy medications will be recorded on the *Concomitant Medication Log* CRF. Documentation of perioperative medications and anesthetic agents is only required for steroids and for medications used to treat an intraoperative adverse event.

Additionally, all epilepsy medications that the subject took in the year preceding the Baseline visit will be recorded on the *Epilepsy Medication Log* CRF. Collection of retrospective rescue medication use is not required.

AEDs

No changes in AED total daily doses are allowed between the Baseline visit and the Month 12 visit with the following exceptions: (1) temporary periprocedural discontinuation or modification for clotting considerations (e.g., valproic acid/valproate), (2) if the clinical condition of the subject warrants modification/discontinuation.

If there is a change, record the changes on the *Epilepsy Medication CRF* and document on a *Protocol Deviation CRF*.

Acute (Rescue) AEDs

In many epilepsy centers, a standard of care for uncontrolled epilepsy is the use of intermittent “rescue” medications (e.g., acute benzodiazepines). These medications are used by the subject on an “as needed” basis to either abort a prolonged seizure or to prevent a cluster of seizures from occurring. If the protocol excluded subjects who used rescue medications the subject pool would decrease substantially. Therefore, the protocol will allow the use of rescue medications during the study. Rescue medications will be recorded on the *Epilepsy Medication CRF*.

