6.3.1 Study Inclusion Criteria

Subjects must meet all of the following inclusion criteria:

1. Diagnosis of unilateral medial temporal lobe epilepsy (MTLE) confirmed clinically and with either (1) ictal scalp recording and MRI evidence of mesial temporal sclerosis or (2) intracranial ictal onset consistent with hippocampal origin
2. Subject's seizures are distinct, stereotypical events that can be reliably counted.
3. Based on medical record, history of an average of at least 1 complex partial or secondarily generalized seizure compatible with MTLE per month for a minimum of the last 12 months prior to the Baseline visit (i.e., at least 12 qualifying seizures in the 12 months prior to the Baseline visit). *(Seizures occurring during inpatient assessment in an epilepsy monitoring unit should not be included in the average).*
4. Subject is on stable antiepileptic drugs (AEDs) for 30 days prior to the Baseline visit and compliant with medication use (as reported by the subject). Stable is defined as no new or discontinued AEDs and no changes to AED total daily dose. *(Exception: (1) temporary changes or discontinuation of AEDs for the purposes of diagnostic or medical procedures during the 30 days preceding the Baseline visit and (2) acute, intermittent use of benzodiazepines or other rescue medications.)*
5. Subject has met the criteria for a medial temporal lobe resection based on the Site's standardized pre-surgical evaluation.
6. Subject is deemed a LITT candidate by the center's epilepsy evaluation team.
7. Subject is 18 years or older at the time of consent.
8. Subject can be reasonably expected to maintain a seizure diary alone or with the assistance of a caregiver.
9. If female, must be postmenopausal, surgically sterile, or, if of childbearing potential, have a serum pregnancy test with a negative result at the Baseline visit and practicing effective contraception.³
10. Subject or legally authorized representative is able to provide appropriate consent to participate.
11. Subject is able to complete regular office and telephone appointments per the protocol requirements.
12. Subject speaks English or Spanish as a primary language. If Spanish, the Site must be able to provide a translated (IRB-approved) consent form and the Site's neuropsychologist must be willing and able to assess the subject in Spanish.

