- A calendar to record daily seizure activity and missed AED doses
- Other relevant information (e.g., new type of seizure)

Subjects may prefer to use their own diary format (paper or electronic); these will be allowed as long as the subject's diary collects the information listed above.

Subjects may also use the diary to record the following (although this information may be elicited by direct questioning of the subject during a study visit):

- Changes to epilepsy and non-epilepsy medications
- Use of rescue medications
- Recording of non-study-related visits to the doctor, hospital or emergency room.
- Comments section to record other relevant information (e.g., new type of seizure)

Instruction for Diary Completion

At the Baseline visit, and again prior to discharge, the investigator or authorized delegate will instruct the subject/caregiver on proper diary completion. This instruction will include:

- Importance of accurate diary-keeping
- Explanation of the seizure classification key
- How to complete the diary:
 - Recording of seizure activity
 - If no seizures occurred on that day, the subject will be instructed to tick the "no seizure" box for that day
 - If subject missed any dose(s) of their epilepsy medications, the subject will be instructed to tick the "missed epilepsy dose" box for that day
 - Explanation that the NAV (not available) designation on a calendar day is for investigator use only
 - How to record medication changes and use of rescue medications
 - How to record non-study-related visits to the doctor, hospital or emergency room
 - What might be recorded in the "other" section

Recording Seizures

Subjects or their caregiver will keep a seizure diary starting the day after discharge. A new diary is provided at subsequent appointments. The subject or caregiver will record the number and type of seizures each day.

Sites will be instructed to take measures to ensure that diary entries are faithfully recorded in order to minimize missing diary data. Subjects will be trained on the importance of accurate diary-keeping.

At each visit the investigative staff will review the diary with the subject and/or caregiver and address any concerns with diary completion. If seizure information is not available for a specific diary day, the coordinator will tick the “NAV” box for that day. An example of a diary day is shown below.

Sun _____	 NAV
 Missed epilepsy dose	

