measured as the number of completed diary days without a seizure since the most recent post-treatment seizure or the beginning of the time period being characterized (e.g. since the day of treatment for the cumulative analysis), whichever is more recent. The longest seizure-free interval will also be calculated for the baseline period, which permits calculation of the change in the longest seizure-free interval from baseline for each subject. The change in longest seizure-free interval may be characterized with descriptive statistics.

Rescue medication use will be analyzed with both a Kaplan-Meier analysis to describe the freedom from use of any rescue medication and a descriptive statistics analysis of the frequency of rescue medication use (number of occasions that rescue medication is required / follow-up time). These analyses will be performed using the same methods as the freedom from seizures and seizure frequency analyses above, but with rescue medication use as the event for analysis rather than seizures.

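### The SAP's rescue-medication analyses have no usable pre-LITT baseline and do not separate prior users from non-users, so the rescue-free curve cannot be read as an effect of LITT

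*Protocol*

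**What the plan says.** **What the SAP will report.** SAP 11.1.3, under seizure outcomes: "Rescue medication use will be analyzed with both a Kaplan-Meier analysis to describe the freedom from use of any rescue medication", together with a frequency (occasions of use over follow-up time). On method: "These analyses will be performed using the same methods as the freedom from seizures and seizure frequency analyses above". The seizure-frequency methods include an optional change and a relative change from the pre-treatment rate. SAP section 10 takes the Treated Set as the main basis for conclusions on performance. Nothing limits the rescue analyses to prior users or stratifies them by prior use.

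**What the protocol collects before LITT.** Appendix A covers the year before Baseline: "all epilepsy medications that the subject took in the year preceding the Baseline visit will be recorded". It then exempts rescue drugs: "Collection of retrospective rescue medication use is not required". Appendix B starts the diary on the day after discharge.

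**Who may use rescue drugs.** Inclusion criterion 4 (section 6.3.1) lists "acute, intermittent use of benzodiazepines or other rescue medications" among the exceptions to the stable-drug rule. Appendix A adds: "Therefore, the protocol will allow the use of rescue medications during the study". Such use is permitted but not required.

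**How use is captured during the study.** Appendix A: "Rescue medications will be recorded on the" Epilepsy Medication CRF. Appendix B makes the diary entry optional: "Subjects may also use the diary to record the following (although this information may be elicited by direct questioning of the subject" at a visit).

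**Versions.** The SAP, dated August 2017, lists protocol Revision A as its source. Its Table 1 has visits from Week -12 to Week 0 with diaries and medication review. The current protocol is Revision B (November 2017), whose schedule has no such phase.

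**The concern.** A method built for seizures is being applied to an event that behaves differently. Every subject must have had at least 12 qualifying seizures in the year before Baseline, so every subject has seizures to become free of. That is not true of rescue use. An unknown share of subjects may never have taken a rescue drug. If they stay off it, they sit at the top of the Kaplan-Meier curve for the whole study, whatever LITT does.

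Without a record of prior use, the reader cannot separate subjects who stopped needing rescue drugs from those who never used them. A rescue rate after LITT likewise has no required pre-LITT rate to set beside it. In a single-arm study the patient's own history is the only internal comparison, so a high rescue-free proportion could be mistaken for benefit.

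**Working it through.** **Inputs**

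- Planned sample: 30 treated subjects (Protocol 10.2.4). The only design figure in the documents is the approximately 80% chance of seeing a 5% event at least once: 1 − 0.95^30 = 0.785, which agrees. Nothing below depends on it, and no figure is given for rescue use.
- Baseline to LITT: within 30 days (Protocol 7.1), or longer if neuropsychological scheduling needs it (Table 1 footnote).
- Horizon: 24 study months of 28 days = 672 days (SAP 12.3). Dropping the first 4 weeks, as in the seizure curve, leaves 644 days.
- Share of never-users, f: not in the documents; assumed 0 to 0.8.
- True rescue-free proportion among prior users, s: not in the documents; 0.30 used for illustration.
- Users' rescue frequency: not in the documents; ranges shown.

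**Step 1. Can the Baseline-to-LITT window serve as a baseline?** With Poisson use at m occasions per month, P(no use in 30 days) = exp(−m × 30/30.44).

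| m per month | P(no use seen) |
|---|---|
| 0.25 | 78% |
| 0.5 | 61% |
| 1 | 37% |
| 2 | 14% |

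Many true users would look like non-users, so the window cannot classify subjects reliably.

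**Step 2. What never-users do to the curve.** If never-users stay rescue-free, the reported proportion is f + (1 − f) × s. With s = 0.30:

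| f | Reported rescue-free | Prior users out of 30 |
|---|---|---|
| 0 | 30% | 30 |
| 0.2 | 44% | 24 |
| 0.4 | 58% | 18 |
| 0.6 | 72% | 12 |
| 0.8 | 86% | 6 |

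Each extra 10% of never-users adds 0.10 × (1 − s), here 0.10 × 0.70 = 7 points.

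**Step 3. Reading the curve backwards.** If 60% are observed rescue-free, the proportion among prior users is (0.60 − f)/(1 − f). This is 60%, 50%, 33% or 0% for f = 0, 0.2, 0.4 or 0.6. One curve fits very different results in the subjects who matter.

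**Step 4. No LITT effect at all.** With r occasions per 84 days and no new users, freedom at 24 study months is f + (1 − f) × exp(−r × 644/84), where 644/84 = 7.667.

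| r per 84 days | exp term | f = 0.3 | f = 0.5 | f = 0.7 |
|---|---|---|---|---|
| 0.5 | 0.022 | 32% | 51% | 71% |
| 0.2 | 0.216 | 45% | 61% | 76% |

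At r = 0.2, even a group made up only of prior users would show 22% freedom with no effect. Yes/no status is therefore not enough; the frequency of prior use is needed too.

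**Step 5. Dating events on study.** The seizure curve takes its events and censoring from the diary. A completed diary day shows that seizures were recorded, but the rescue entry is optional, so the day need not be rescue-free. Medication review is scheduled at Discharge, Day 14 and every monthly visit or call, but it is not among the Early Withdrawal assessments (Protocol 7.8 and Table 2).

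**The case against.** The case on the other side has substance.

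- **Pre-LITT use is not barred from collection.** A reader might infer that no rescue information before LITT can exist. The documents do not support that. Appendix A says only that retrospective collection is not required. Baseline includes a medication review, and use between Baseline and LITT can go on the Epilepsy Medication CRF. This stands, but Step 1 shows that the window is too short to be a baseline.
- **Change from baseline is not a commitment.** SAP 11.1.3 defines rescue frequency over follow-up time alone, and change from baseline is optional even for seizures. A reader might infer that a planned analysis is impossible. More exactly, an optional analysis reached through the shared-methods sentence has no required baseline data.
- **On-study capture is better than the diary wording suggests.** Direct questioning, medication review at scheduled contacts, and diary training that covers rescue use all help. This stands. What remains is the source used to date events and censoring.
- **The analyses are descriptive.** They fall under a secondary endpoint in a study without formal hypothesis tests, and no passage claims a rescue benefit. This limits the priority but does not make the curve interpretable.
- **The cause is largely a version mismatch.** Under the SAP's own schedule a prospective 12-week period preceded LITT. This is correct and belongs in the fix.

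**Conclusion.** The point holds in a limited form. The planned rescue analyses have no usable pre-LITT baseline, and never-users who stay off rescue drugs count as rescue-free. Neither the curve nor the rate can then be read as an effect of LITT.

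The marginal size is 0.10 × (1 − s) per 10% of never-users, assuming that they stay off rescue drugs. The total is unknown because it depends on the never-user share and on how often users take rescue drugs. A reader might infer from the 0.5-per-84-days row in Step 4 that the curve is essentially the never-user share. The documents do not establish that: at 0.2 per 84 days the same formula gives 45%, 61% and 76% for shares of 30%, 50% and 70%, and at a 10% share with 0.5 per 84 days it gives only 0.10 + 0.90 × 0.022 = 12%. The one hint in Appendix A, that excluding rescue users would shrink the pool substantially, suggests that users are common but gives no share.

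The primary endpoint and the sample-size statement are unaffected. This is a worthwhile, inexpensive improvement.

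**What to change.** 1. **Protocol Appendix A.** Replace the sentence that waives retrospective rescue data. At Baseline, record prior rescue use (yes/no) and the number of occasions over the same retrospective window as the seizure count. Twelve months of seizure counts and epilepsy medications are already sought at that visit.
2. **SAP 11.1.3, reporting.** Give the rescue Kaplan-Meier curve and rates separately for prior users and non-users. Base any statement on freedom from, or reduction in, rescue use on prior users.
3. **SAP 11.1.3, dating.** Take rescue events and censoring from the medication review and the Epilepsy Medication CRF, not from completed diary days alone. A diary tick box is optional, since subjects may keep their own diary format.
4. **Where baseline data cannot be obtained.** State that the rescue summaries are not evidence of change after LITT.
5. **SAP as a whole.** Update it to protocol Revision B, including its references to a 12-week or 3-month baseline phase.

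The cost is one or two Baseline fields and some SAP wording. The downsides are that recalled use is imprecise and that the prior-user group will be smaller than 30 (for example 18 if f = 0.4, 12 if f = 0.6). These changes concern data collection and reporting only; they do not touch who may take rescue medication or when.
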